## **11.4 Patient Confidentiality**

The Investigator and Sponsor must ensure that the patient's confidentiality is maintained. On the case report forms or other documents submitted to the Sponsor or designee, patients should be identified by initials (if permitted by local law) and a patient identification number only.

Documents that are not for submission to the Sponsor or designee (e.g., signed informed consent forms) should be kept in strict confidence by the Investigator.

In compliance with Federal and local regulations/ICH GCP Guidelines, it is required that the Investigator and institution permit authorized representatives of the company, of the regulatory agency(s), and the IEC/IRB direct access to review the patient's original medical records for verification of study-related procedures and data. Direct access includes examining, analyzing, verifying, and reproducing any records and reports that are important to the evaluation of the study. The Investigator is obligated to inform and obtain the consent of the patient to permit named representatives to have access to his/her study-related records without violating the confidentiality of the patient.

## **12. ADMINISTRATIVE AND LEGAL OBLIGATIONS**

### **12.1 Protocol Amendments**

Protocol amendments must be made only with the prior approval of the Sponsor or designee. Agreement from the Investigator must be obtained for all protocol amendments and amendments to the informed consent document. The regulatory authority and IEC/IRB must be informed of all amendments and give approval for any amendments likely to affect the safety of the patients or the conduct of the trial. The Investigator must send a copy of the approval letter from the IEC/IRB to the Sponsor or designee.

### **12.2 Study Termination**

The Sponsor or designee reserves the right to terminate the study. The Investigator reserves the right to terminate their participation in the study, according to the terms of the site contract. The Investigator/Sponsor or designee should notify the IEC/IRB in writing of the trial's completion or ET. An Investigator who terminates participate is required to send a copy of the IEC/IRB notification to the Sponsor or designee.

### **12.3 Study Documentation and Storage**

Source documents are original documents, data, and records from which the patient's case report form data are obtained. These include but are not limited to hospital records, clinical and office charts, laboratory and pharmacy records, diaries, imaging, and correspondence. In this study, eCRF may not be used as source documents.

The Investigator and Study Center staff are responsible for maintaining a comprehensive and centralized filing system of all study-related (essential) documentation in accordance with Section 8 of the ICH Guidelines (E6), suitable for inspection at any time by representatives from the Sponsor or designee and/or applicable regulatory authorities. Elements should include:

- Patient files containing completed case report forms, informed consents, and supporting copies of source documentation
- Study files containing the protocol with all amendments, Investigator's Brochure, copies of pre-study documentation and all correspondence to and from the IEC/IRB and the Sponsor or designee

- If drug supplies are maintained at the Study Center, proof of receipt, Study Drug Product Accountability Record, Return of Study Drug Product for Destruction, final Study Drug product reconciliation, and all drug-related correspondence

In addition, all original source documents supporting entries in the case report forms must be maintained and be readily available for the duration required by GCP or local regulatory requirements, whichever is longer.

No study document should be destroyed without prior written agreement between the Sponsor or designee and the Investigator. Should the Investigator wish to assign the study records to another party or move them to another location, he/she must notify the Sponsor or designee, in accordance with GCP.

#### **12.4 Study Monitoring**

The Sponsor representative and regulatory authority inspectors are responsible for contacting and visiting the Investigator for the purpose of inspecting the facilities and, upon request, inspecting the various records of the trial (e.g., case report forms and other pertinent data) provided that patient confidentiality is respected.

The Sponsor monitor or designee is responsible for inspecting the case report forms at regular intervals throughout the study to verify adherence to the protocol; completeness, accuracy, and consistency of the data; and adherence to local regulations on the conduct of clinical research. The monitor should have access to patient medical records and other study-related records needed to verify the entries on the case report forms. Source data should be attributable, legible, contemporaneous, original, and accurate (ALCOA) and must meet the regulatory requirements for recordkeeping.

The Investigator agrees to cooperate with the monitor to ensure that any problems detected in the course of these monitoring visits, including delays in completing case report forms, are resolved.

In accordance with ICH GCP and the Sponsor's audit plans, this study may be selected for audit by representatives from the Sponsor's Clinical Quality Assurance Department (or designees). Inspection of Study Center facilities (e.g., pharmacy, drug storage areas, laboratories) and review of study-related records will occur to evaluate the trial conduct and compliance with the protocol, ICH GCP, and applicable regulatory requirements.

To ensure the quality of clinical data a clinical data management review will be performed on patient data received by the Sponsor or designee. During this review, patient data will be checked for consistency, omissions, and any apparent discrepancies. In addition, the data will be reviewed for adherence to the protocol and GCP. To resolve any questions arising from the clinical data management review process, data queries and/or Study Center notifications will be sent to the Study Center for completion and return to Sponsor or designee.

The Principal Investigator will sign and date the indicated places on the case report form. These signatures will indicate that the Principal Investigator inspected or reviewed the data on the case report form, the data queries, and the Study Center notifications, and agrees with the content in accordance with the general investigational plan.

### **12.5 Language**

Case report forms must be completed in English. Whenever possible, the trade name rather than the generic name for concomitant medications should be recorded and if possible, in English. Generic names are acceptable if the trade name is unknown. Combination medications should be recorded using their trade name in English if possible.

All written information and other material to be used by patients and investigative staff must use vocabulary and language that are clearly understood.

### **12.6 Compensation for Injury**

The Sponsor maintains appropriate insurance coverage for clinical trials and will follow applicable local compensation laws. Patients will be treated and/or compensated for any study-related illness/injury in accordance with the information provided in the Compensation for Injury section of the Informed Consent document.

## **14. APPENDICES**

## **Appendix A    Schedule of Procedures**

[Schedule of Procedures for Weekly and Every 2-Week Dosing Cohorts](#)

[Schedule of Procedures for Every 4-Week Dosing Cohorts](#)

**Appendix A Schedule of Procedures – Weekly and Every 2-Week Dosing**

	Screen	Treatment Period																			Follow-up Period			
Study Week	-4 to -1	1	1	5	9	13	17	21	25	27			29	33	37	41	45	49	53/ET	4*	10*	16*		
Study Day	-28 to -1	1	2 a	29	57	85	113	141	169	183	184 a	185 a	197	225	253	281	309	337	365	*Post Last Dose				
Visit Window +/- Days	0	-3 b	0	2	2	2	3	3	3	3	0	0	3	3	3	3	3	3	3	3	3	3		
Informed Consent	X																							
Outpatient Visit	X	X	X	X	X	X	X	X	X	X	X	X	X	X	X	X	X	X	X	X	X	X		
Inclusion/Exclusion Criteria	X	X																						
Medical History c	X																							
Vital Signs	X	X		X	X	X	X	X	X	X			X	X	X	X	X	X	X	X	X	X		
Physical Examination	X	X		X		X		X		X				X		X		X	X	X	X	X		
Body Weight and Height d	X									X						X						X		
12- lead ECG (triplicate)	X	X		X		X		X		X				X		X		X	X	X	X	X		
24-Hour Urine for Creatinine Clearance and Protein	X																							
Extended Urinalysis e	X	EXTENDED URINALYSIS PERFORMED EVERY 14 DAYS e, f																			X	X	X	
Renal Biomarkers g	X	RENAL BIOMARKERS PERFORMED EVERY 14 DAYS f, g																			X h	X h	X h	
Serum Creatinine and Cys-C i, j		SERUM CREATININE and Cys-C PERFORMED EVERY 14 DAYS f, i																			X	X	X	
Genetic Testing		X																						
Chemistry Panel j, k	X	EVERY 14 DAYS f					X	X	X	X			X	X	X	X	X	X	X	X	X	X	X	
Hematology j, k	X	HEMATOLOGY PERFORMED EVERY 14 DAYS f, k																				X h	X h	X h
Platelet Function		X		X	X	X	X	X	X	X			X	X	X	X	X	X	X	X	X	X		
Coagulation	X	X								X														
Hepatitis B, C, HIV	X																							
Thyroid Panel	X																							
hsCRP		X								X									X			X		
Plasma PK - ISIS 681257 l		X 	X 	X	X	X	X	X	X	X 	X 	X 	X		X				X	X	X	X		
ISIS 681257 Antibodies		X		X	X	X				X									X			X		

**Appendix A Schedule of Procedures – Weekly and Every 2-Week Dosing *Continued***

Study Week	Screen	Treatment Period																		Follow-up Period		
	-4 to -1	1	1	5	9	13	17	21	25	27			29	33	37	41	45	49	53/ET	4*	10*	16*
Study Day	-28 to -1	1	2 a	29	57	85	113	141	169	183	184 a	185 a	197	225	253	281	309	337	365	*Post Last Dose		
Visit Window +/- Days	0	-3 b	0	2	2	2	3	3	3	3	0	0	3	3	3	3	3	3	3	3	3	3
FSH (women only, if applicable) i, m	X																					
Serum Pregnancy Test m	X	X			X		X		X						X		X		X	X	X	X
Archived Serum & Plasma Samples j, n		X			X		X			X					X		X		X	X	X	X
PD Panel i	X	X		X	X	X	X	X		X			X		X		X		X	X	X	X
Lipid Panel i	X	X		X	X	X	X	X		X			X		X		X		X	X	X	X
Lp(a) Characterization		X																				
Study Drug: SC Injection	WEEKLY AND EVERY 2-WEEK SUBCUTANEOUS ADMINISTRATION OF STUDY DRUG (Week 1 through Week 53/Day 365) o																					
Adverse Events	X	X	X	X	X	X	X	X		X	X	X	X	X	X	X	X	X	X	X	X	X
Concomitant Medication	X	X	X	X	X	X	X	X		X	X	X	X	X	X	X	X	X	X	X	X	X

All procedures and study samples are to be done pre-dose at respective visits, unless specified

- a Visit only required for patients in PK subgroup.
- b Day 1/Baseline assessments can be performed up to 3 days (-3 days) prior to the actual Day 1 visit, which is the day of first Study Drug dose.
- c Patient charts will be reviewed in order to collect disease associated medical history data such as CVD history.
- d Height only required at Screening.
- e All tests listed in Appendix B under Extended Urinalysis should be performed, including routine urinalysis, urine microscopy, UACR and UPCR.
- f Assessments and procedures to be conducted by either a home healthcare service or the Study Center. Patient Study Center visits must be no more than 4 weeks apart during the treatment period.
- g Urine samples for renal biomarkers will be collected. Sample analysis will be conducted in accordance with Safety Monitoring for Renal Function (Section 8.5.2).
- h During follow-up period, hematology sampling for platelet values and urine renal biomarker samples are taken every 14 days for 6 weeks after last dose of Study Drug, then every 6 weeks.
- i Serum Creatinine and Cys-C will be collected as a part of chemistry panel at visits when chemistry panel is performed, or as stand-alone samples at time points when a chemistry panel is not performed.

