Following SC administration, ISIS 681257 was absorbed rapidly into the systemic circulation, with median time to maximum plasma concentrations ( $T_{max}$ ) ranging from 1 to 4 hours. Similar  $T_{max}$  values were observed at all dose levels. Maximum observed plasma concentrations ( $C_{max}$ ) and  $AUC_{0-24hr}$  were dose-dependent over the studied SC dose range. The mean peak ( $C_{max}$ ) and total exposure ( $AUC_{0-24hr}$ ) increased proportionally with dose at dose levels ranging from 10 to 40 mg, and greater than dose proportionally at dose levels ranging from 40 to 120 mg.

After reaching  $C_{max}$ , mean plasma concentrations of ISIS 681257 declined in a biphasic fashion over time, with an initial, relatively fast distribution phase that dominated the plasma clearance followed by a slower elimination phase. Characterization of the terminal elimination phase yielded an apparent terminal elimination half-life of approximately 3 to 4 weeks over a dose range of 10 to 120 mg (either single- or multiple-dose), and appeared to be independent of dose. This result is consistent with the slow elimination of ISIS 681257 observed from monkey tissues, and the comparatively long elimination half-lives observed for this chemical class.

Plasma trough concentrations (168 hours or 7 days from previous dose) monitored during the treatment period in the multiple-dose cohorts increased with increasing dose, consistent with expectations (based on preclinical assessments and experience with other compounds of this chemical class) that trough plasma concentrations reflect exposure in tissues. Plasma trough concentrations did not increase greatly after the loading period (Day 15), suggesting that accumulation in major tissues of distribution had approached steady-state after the loading period.

Overall, the human PK of ISIS 681257 are consistent with the expected PK for compounds within this chemical class.

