#### **9.5.4 Contraception and Pregnancy**

Male and female patients of childbearing potential must continue to use appropriate contraception with their partners, or refrain from sexual activity, as described in [Section 6.3.1](#).

If a patient becomes pregnant or a pregnancy is suspected, or if a male patient makes or believes that he has made someone pregnant during the study, then the Study Center staff must be informed immediately. An Initial Pregnancy Form should be submitted to the Sponsor or designee **within 24 hours** of first learning of the occurrence of pregnancy. Follow-up information including delivery or termination is reported by designating as ‘Follow-up’ on the Pregnancy Forms and reported within 24 hours of occurrence.

Payment for all aspects of obstetrical care, child or related care will be the patient’s responsibility.

Female patients: If a suspected pregnancy occurs while on the study (including during the follow-up period), a pregnancy test will be performed. The patient with a confirmed pregnancy will be immediately withdrawn from treatment with Study Drug. However, the patient will be encouraged to complete the Post-treatment Follow-up portion of the study to the extent that study procedures do not interfere with the pregnancy. Regardless of continued study participation, the Investigator will assist the patient in getting obstetrical care and the progress of the pregnancy will be followed until the outcome of the pregnancy is known (i.e., delivery, elective termination, or spontaneous abortion). If the pregnancy results in the birth of a child, the Study Center and Sponsor may require access to the mother and infant’s medical records for an additional 8 weeks after birth. Follow-up will be performed to the extent permitted by the applicable regulations and privacy considerations.

Male patients: The progress of the pregnancy of a male patient’s partner should be followed until the outcome of the pregnancy is known (i.e., delivery, elective termination, or spontaneous abortion). If the pregnancy results in the birth of a child, **the Study Center and Sponsor may request access to the mother and infant’s medical records for an additional 8 weeks after birth.** Follow-up will be performed to the extent permitted by the applicable regulations and privacy considerations.

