**Appendix A Schedule of Procedures – Every 4-Week Dosing *Continued***

	Screen	Treatment Period																			Follow-up Period			
Study Week	-4 to -1	1	1	5	9	13	17	21	25		26	27	29	33	37	41	45	49	53/ET	4*	10*	16*		
Study Day	-28 to -1	1	2 a	29	57	85	113	141	169	170 a	171 a	176 a	183 a	197	225	253	281	309	337	365	*Post Last Dose			
Visit Window +/- Days	0	-3 b	0	2	2	2	3	3	3	0	0	3	3	3	3	3	3	3	3	3	3	3	3	
FSH (women only, if applicable) i, m	X																							
Serum Pregnancy Test m	X	X		X	X	X	X	X	X					X	X	X	X	X	X	X	X	X	X	
Archived Serum & Plasma Samples j, n		X		X		X		X					X		X		X		X		X	X	X	
PD Panel l	X	X		X	X	X	X	X	X				X	X		X		X		X	X	X	X	
Lipid Panel l	X	X		X	X	X	X	X	X			X	X	X		X		X		X	X	X	X	
Lp(a) Characterization		X																						
Study Drug: SC Injection		EVERY 4-WEEK SUBCUTANEOUS ADMINISTRATION OF STUDY DRUG (Week 1 through Week 49/Day 337) o																						
Adverse Events	X	X	X	X	X	X	X	X	X	X	X			X	X	X	X	X	X	X	X	X	X	
Concomitant Medication	X	X	X	X	X	X	X	X	X	X	X			X	X	X	X	X	X	X	X	X	X	

All procedures and study samples are to be done pre-dose at respective visits, unless specified

- a Visit only required for patients in PK subgroup.
- b Day 1/Baseline assessments can be performed up to 3 days (-3 days) prior to the actual Day 1 visit, which is the day of first Study Drug dose.
- c Patient charts will be reviewed in order to collect disease associated medical history data such as CVD history.
- d Height only required at Screening.
- e All tests listed in Appendix B under Extended Urinalysis should be performed, including routine urinalysis, urine microscopy, UACR and UPCR.
- f Assessments and procedures to be conducted by either a home healthcare service or the Study Center. Patient Study Center visits must be no more than 4 weeks apart during the treatment period.
- g Urine samples for renal biomarkers will be collected. Sample analysis will be conducted in accordance with Safety Monitoring for Renal Function (Section 8.5.2).
- h During follow-up period, hematology sampling for platelet values and urine renal biomarker samples are taken every 14 days for 6 weeks after last dose of Study Drug, then every 6 weeks.

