**Appendix A Schedule of Procedures – Every Week and Every 2-Week Dosing *Continued***

Study Week	Screen	Treatment Period																			Follow-up Period		
	-4 to -1	1	1	5	9	13	17	21	25	27			28	29	33	37	41	45	49	53/ET	4*	10*	16*
Study Day	-28 to -1	1	2 j	29	57	85	113	141	169	183	184 l	185 j	190 o	197	225	253	281	309	337	365	*Post Last Dose		
Visit Window +/- Days	0	-3 a	0	2	2	2	3	3	3	3	0	0	3	3	3	3	3	3	3	3	3	3	3
FSH (women only, if applicable) e, g	X																						
Serum Pregnancy Test g	X	X			X		X		X							X		X		X	X	X	X
Archived Serum & Plasma Samples e, h		X			X		X			X						X		X		X	X	X	X
PD Panel e	X	X		X	X	X	X	X		X				X		X		X		X	X	X	X
Lipid Panel e	X	X		X	X	X	X	X		X				X		X		X		X	X	X	X
Lp(a) Characterization		X																					
Study Drug: SC Injection		WEEKLY SUBCUTANEOUS ADMINISTRATION OF STUDY DRUG (Week 1 through Week 53/Day 365)k																					
Adverse Events	X	X	X	X	X	X	X	X		X	X	X		X	X	X	X	X	X	X	X	X	X
Concomitant Medication	X	X	X	X	X	X	X	X		X	X	X		X	X	X	X	X	X	X	X	X	X

All procedures and study samples are to be done pre-dose at respective visits, unless specified

- a Day 1/Baseline assessments can be performed up to 3 days (-3 days) prior to the actual Day 1 visit, which is the day of first Study Drug dose.
- b Assessments and procedures to be conducted by either a home healthcare service or the Study Center. Patient Study Center visits must be no more than 4 weeks apart during the treatment period.
- c Patient charts will be reviewed in order to collect disease associated medical history data such as CVD history.
- d Height only required at Screening.
- e Blood samples to be collected after an overnight fast of at least 10 hours and preferably not more than 12 hours.
- f If the platelet value, serum creatinine or liver enzyme tests are uninterpretable (e.g., due to clumping, hemolysis or quantity not sufficient) a repeat blood specimen should be re-drawn as soon as possible (ideally within 7 days). All platelet count results will be reviewed promptly (within 48 hours of receipt) by the Investigator as per Section 6.2.1. Any case of a platelet count  $\leq 50,000/\text{mm}^3$  should be reported in an expedited fashion to the Sponsor.
- g Women who are not surgically sterile or post-menopausal.

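### Pregnancy is tested every 4 weeks in the every-4-week cohorts but only every 8 weeks, with one 12-week gap, in the weekly and 2-weekly cohorts, which are dosed most often

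*Protocol*

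**What the plan says.** Appendix A of the protocol (Amendment 4) has one schedule for the weekly and 2-weekly cohorts (D and E) and one for the every-4-week cohorts (A, B and C). Both have the row "Serum Pregnancy Test m", and in both tables footnote m limits the test to women who are neither surgically sterile nor post-menopausal.

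- **Cohorts D and E:** Screening, Day 1, Weeks 9, 17, 25, 37, 45 and 53/ET.
- **Cohorts A to C:** Screening, Day 1, Weeks 5, 9, 13, 17, 21, 25, 29, 33, 37, 41, 45, 49 and 53/ET.
- **Both:** 4, 10 and 16 weeks after the last dose.

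On the consequence of a positive test, Section 9.5.4 says: "The patient with a confirmed pregnancy will be immediately withdrawn from treatment with Study Drug". Section 8.8 likewise lists pregnancy as a reason for permanent discontinuation. Section 9.5.4 also calls for a test whenever pregnancy is suspected, but sets no routine interval. The routine interval is therefore fixed by Appendix A alone.

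**The concern.** The two schedules cover the same drug and the same class of women, yet the cohorts with more frequent injections have the sparser testing. Nothing in the protocol explains this.

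The scheduled test is the only one that can find a pregnancy nobody suspects. Because a confirmed pregnancy stops dosing, the interval between tests limits how long such a pregnancy could go on being exposed. Cohort E has weekly dosing and the highest total dose in the study (up to 1040 mg, Table 2), and it shares the longest interval with Cohort D. Drug also persists after stopping: Section 2.3.4 reports an "apparent terminal elimination half-life of approximately 3 to 4 weeks". Section 8.1 permits self-administration, so doses may be given with no clinic contact.

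Two features of the Cohort D and E row suggest an oversight rather than a choice. Its 8-weekly rhythm breaks once, because Week 33 has no test. And these women are tested more often after stopping the drug, at most 6 weeks apart, than while taking it.

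**Working it through.** **Inputs.** The marks come from the pregnancy-test row of each Appendix A schedule, read against that table's own study-day header. Doses and dosing intervals come from Section 8.1 and Table 2. Appendix A has procedures done before dosing unless specified, so a dose due on a test day falls after that test.

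**Step 1: intervals between consecutive treatment-period tests (difference in study days ÷ 7).**

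| Cohorts | Test days | Intervals (weeks) |
|---|---|---|
| D, E | 1, 57, 113, 169, 253, 309, 365 | 8, 8, 8, 12, 8, 8 |
| A to C | 1, 29, 57, 85, 113, 141, 169, 197, 225, 253, 281, 309, 337, 365 | 4, thirteen times |

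The long interval is (253 − 169) ÷ 7 = 12 weeks, Week 25 to Week 37. Tests after Day 1 number 6 and 13.

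**Step 2: is the row misread?** The D and E row has 22 cells for 22 visit columns, and the A to C row has 23 for 23. Matching counts alone do not prove alignment. The superseded Amendment 3 schedule for D and E (row "Serum Pregnancy Test g") has an additional Week 28 column, so 23 columns, and its marks fall on the same study days. The Amendment 3 row for A to C also agrees. A shifted row would be unlikely to agree across differently laid-out tables.

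**Step 3: doses between one test and the next, at full dosing.** Number of doses × dose:

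| Cohort | Usual interval | Week 25 to 37 |
|---|---|---|
| C | 1 × 60 = 60 mg | 1 × 60 = 60 mg between any two tests (tests stay 4-weekly) |
| D | 4 × 20 = 80 mg | Weeks 25, 27, 29, 31, 33, 35: 6 × 20 = 120 mg |
| E | 8 × 20 = 160 mg | Weeks 25 to 36: 12 × 20 = 240 mg |

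**Step 4: could visit burden explain it?** No. Appendix A marks an outpatient visit for Cohorts D and E at Weeks 5, 13, 21, 29, 33, 41 and 49. Footnote f adds that "Patient Study Center visits must be no more than 4 weeks apart during the treatment period". Blood is already drawn between and at these visits: "SERUM CREATININE and Cys-C PERFORMED EVERY 14 DAYS".

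**Step 5: effect of the change.** With 4-weekly tests in D and E, tests after Day 1 rise to 6 + 7 = 13, and the longest interval falls from 12 to 4 weeks. Doses between tests fall to 2 × 20 = 40 mg in D and 4 × 20 = 80 mg in E. Adding Week 33 alone gives intervals of 8, 8, 8, 8, 4, 8 and 8 weeks, so the longest becomes 8.

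**The case against.** The strongest reply is that two schedules which differ do not contradict each other. No text promises equal testing or sets a maximum interval: footnote m says who is tested and footnote f limits visit spacing, not test spacing. On that view only the 12-week gap is irregular, and only Week 33 needs adding. It is true that there is no formal contradiction. But the protocol chose 4 weeks for three cohorts under the same rules, and gives no reason for a longer interval where dosing is more frequent.

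Safeguards also exist beyond the scheduled test. Inclusion criterion 7 requires sterility, post-menopausal status, true abstinence or two highly effective contraceptive methods. Suspected pregnancy must be reported at once and tested. Between Weeks 25 and 37, Cohorts D and E attend at Weeks 27, 29 and 33. These lower the absolute risk, but contraception and testing on suspicion apply equally to Cohorts A to C, so they do not explain the difference.

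Three qualifications stand:
- The dose counts are maxima. Only 6 months of treatment is the planned minimum, so the 12-week gap affects only women who continue past Week 25; before that the interval in D and E is 8 weeks.
- More frequent dosing is not always higher exposure. Cohort D's maximum total (520 mg) equals Cohort B's and is below Cohort C's (780 mg); over 12 weeks Cohort C receives 3 × 60 = 180 mg against 120 mg in D. The total-dose argument is specific to Cohort E.
- The half-life does not separate the cohorts, and the protocol as shown cites no reproductive-toxicity finding.

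**Conclusion.** The concern holds. In the current text, women in Cohorts D and E are tested at 8-week intervals with one of 12 weeks, against 4 weeks throughout in Cohorts A to C, with the same eligibility for testing and no stated reason. The size is 6 against 13 treatment-period tests after Day 1, and up to 12 doses in Cohort E or 6 in Cohort D between the Week 25 and Week 37 tests. These figures assume full dosing through Week 37 (for the doses) or attendance through Week 53 (for the test counts), and ignore the visit windows.

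The rating is minor. The protocol does not give the number of women of childbearing potential; in a cardiovascular population aged up to 80 it is probably small. Endpoints, randomization and statistical analysis are unaffected. This is a patient-safety inconsistency that is cheap to remove.

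**What to change.** In the weekly and 2-weekly schedule of Appendix A, mark the serum pregnancy test at Weeks 5, 13, 21, 29, 33, 41 and 49, leaving footnote m unchanged, so that both schedules test every 4 weeks. If the sponsor wants to keep 8-weekly testing in Cohorts D and E, it should at least add Week 33 and state why the interval differs from Cohorts A to C.

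The full change is seven marks in one table row. It needs no new visits and at most 7 extra assays for each woman concerned.
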